9.3. Recording and Follow-Up of Adverse Events and/or Serious Adverse Events

Adverse Event and Serious Adverse Event Recording

- An AE/SAE that begins or worsens after informed consent is signed should be recorded on the Adverse Event Form in the eCRF. Adverse events/SAEs should be reported for enrolled participants, but only SAEs need to be reported for screen failure participants. Conditions that were present at the time informed consent/assent was given should be recorded on the Medical History Form in the eCRF.
- When an AE/SAE occurs, it is the responsibility of the investigator to review all documentation (eg, hospital progress notes, laboratory reports, and diagnostic reports) related to the event.
- The investigator (or delegate) will then record all relevant AE/SAE information in the eCRF.
- It is **not** acceptable for the investigator to send photocopies of the participant's medical records in lieu of completing the Adverse Event Form in the eCRF.
- There may be rare instances when copies of medical records for certain cases are requested. In this case, all participant identifiers, with the exception of the participant number, will be redacted by the site staff on the copies of the medical records before submission. These records can be submitted to Incyte Pharmacovigilance by email/fax per the contact information listed as per SAE Completing Guidelines.
- The investigator will attempt to establish a diagnosis of the event based on signs, symptoms, and/or other clinical information. Whenever possible, the diagnosis (not the individual signs/symptoms) will be documented as the AE/SAE. When a clear diagnosis cannot be identified, each sign or symptom should be reported as a separate AE/SAE.

To the extent possible, each AE/SAE should be evaluated to determine the following:

- The severity grade (CTCAE v5.0 Grade 1 to 5). See below for further instructions on the assessment of intensity.
- Whether there is at least a reasonable possibility that the AE is related to the study cream: suspected (yes) or not suspected (no). See below for further instructions on the assessment of causality.
- The start and end dates, unless unresolved at the final safety follow-up visit.
- The action taken with regard to study cream as a result of the AE/SAE(s).
- The event outcome (eg, not recovered/not resolved, recovered/resolved, recovering/resolving, recovered/resolved with sequelae, fatal, unknown).
- The seriousness, as per the SAE definition provided in Section 9.2.
- The action taken with regard to the event. Note: If an AE is treated with a concomitant medication or nondrug therapy, this action should be recorded on the Adverse Event Form and the treatment should be specified on the appropriate eCRF (eg, Prior/Concomitant Medications, Procedures and Non-Drug Therapy).

Assessment of Intensity

The severity of AEs will be assessed using CTCAE v5.0 Grades 1 through 5. If an event is not classified by CTCAE, the severity of the AE will be graded according to the scale below to estimate the grade of severity.

The investigator will make an assessment of intensity for each AE and SAE reported during the study and assign it to 1 of the following categories:

- **Grade 1:** Mild; asymptomatic or mild symptoms; clinical or diagnostic observations only; treatment not indicated.
- **Grade 2:** Moderate; minimal, local, or noninvasive treatment indicated; limiting age-appropriate activities of daily living.
- **Grade 3:** Severe or medically significant but not immediately life-threatening; hospitalization or prolongation of hospitalization indicated; disabling; limiting self-care activities of daily living.
- **Grade 4:** Life-threatening consequences; urgent treatment indicated.
- **Grade 5:** Fatal.

Assessment of Causality

- The investigator is obligated to assess the relationship between study cream and each occurrence of each AE/SAE.
- A "reasonable possibility" of a relationship conveys that there are medical facts, evidence, and/or arguments to suggest a causal relationship, rather than that a relationship cannot be ruled out.
- The investigator will use clinical judgment to determine the possibility of a relationship.
- The investigator will also consult the Reference Safety Information in the IB for study cream in making his/her assessment.
- Alternative causes, such as underlying or concurrent disease(s), concomitant therapy, and other risk factors, as well as the temporal relationship of the event to study cream administration, will be considered and investigated.
- For each AE/SAE, the investigator **must** document in the medical notes that he/she has reviewed the AE/SAE and has provided an assessment of causality.
- With regard to assessing causality of SAEs:
 - There may be situations in which an SAE has occurred and the investigator has minimal information to include in the initial report. However, the causality assessment is one of the criteria used when determining regulatory reporting requirements. **Therefore, it is very important that the investigator always make an assessment of causality based on the available information for every event before the initial transmission of the SAE.**
 - The investigator may change his/her opinion of causality in light of follow-up information and submit the updated causality assessment.

Follow-Up of Adverse Events and Serious Adverse Events

- The investigator is obligated to perform or arrange for the conduct of supplemental measurements and/or evaluations as medically indicated or as requested by the sponsor to elucidate the nature and/or causality of the AE or SAE as fully as possible. This may include additional laboratory tests or investigations, histopathological examinations, or consultation with other health care professionals.
- Once an AE is detected, it should be followed in the AE eCRFs until it has resolved or until it is judged to be permanent; assessment should be made at each visit (or more frequently if necessary) of any changes in severity, the suspected relationship to the study cream, the interventions required to treat the event, and the outcome.
- When the severity of an AE changes over time for a reporting period (eg, between visits), each change in severity will be reported as a separate AE.
- If a participant dies during participation in the study or during a recognized follow-up period, the investigator will provide the sponsor with a copy of any postmortem findings, including histopathology.
- New or updated SAE information will be recorded in the originally completed eCRF and reported to Incyte Pharmacovigilance (either via email/fax) until resolution, stabilization, the event is otherwise explained, or the participant is lost to follow-up.
- Any updated SAE data (including SAEs being downgraded to nonserious) will be submitted to the sponsor (or designee) within 24 hours of receipt of the information.

9.4. Reporting of Serious Adverse Events

All SAEs, regardless of suspected causality (eg, relationship to study cream or study procedure[s]), occurring after the participant has signed the ICF/assent through 30 days after the last application of study cream, must be reported to the sponsor (or designee) within 24 hours of learning of its occurrence, unless otherwise specified by the Protocol. The investigator will submit any updated SAE data to the sponsor (or designee) within 24 hours of it being available.

Investigators are not obligated to actively seek AE or SAE information after conclusion of study participation (ie, after the safety follow-up visit or 30 days after the last application of study cream). However, if the investigator learns of any SAE, including a death, at any time during this period, and after a participant has been discharged from the study, and he/she considers the event to be reasonably related to the study cream or study participation, the investigator must notify the sponsor (or designee) within 24 hours of becoming aware of the event.

After the initial AE/SAE report, the investigator is required to proactively follow each participant at subsequent visits/contacts. All SAEs will be followed until resolution, stabilization, the event is otherwise explained, or the participant is lost to follow-up (as defined in Section [7.3](#)).

Prompt notification by the investigator to the sponsor of a SAE is essential so that legal obligations and ethical responsibilities toward the safety of participants and the safety of a study cream under clinical investigation are met.

If the SAE is not documented in the Reference Safety Information of the [IB](#) for the study cream (new occurrence) and is thought to be related to the study cream, the sponsor or its designee may urgently require further information from the investigator for reporting to health authorities. The sponsor or its designee may need to issue an Investigator Notification to inform all investigators

involved in any study with the same drug that this SAE has been reported. Suspected unexpected serious adverse reactions will be collected and reported to the competent authorities and relevant ethics committees in accordance with Directive 2001/20/EC or as per national regulatory requirements in participating countries.

The sponsor has a legal responsibility to notify both the local regulatory authority and other regulatory agencies about the safety of a study cream under clinical investigation. The sponsor will comply with country-specific regulatory requirements relating to safety reporting to the regulatory authority, IRB/IEC, and investigators.

Investigator safety reports must be prepared for suspected unexpected serious adverse reactions according to local regulatory requirements and sponsor policy and forwarded to investigators as necessary.

An investigator who receives an investigator safety report describing a SAE or other specific safety information (eg summary or listing of SAEs) from the sponsor will review and then file it along with the Investigator's Brochure and will notify the IRB/IEC, if appropriate, according to local requirements.

Serious Adverse Event Reporting

- Information about all SAEs is collected and recorded on the Adverse Event Form in the eCRF.
- The investigator must report within 24 hours of learning of its occurrence any SAE via the EDC system (primary method) or by completing the Serious Adverse Event Report Form in English (only if the EDC system is not available). The contact information for Incyte Pharmacovigilance by email/fax is listed in the Study Reference Manual or as per the Incyte Reference Guide for Completing the Serious Adverse Event Report Form.
- In circumstances where the EDC system is not accessible for reporting SAE information (initial and/or follow-up SAE information) to the sponsor within 24 hours, refer to the Incyte Reference Guide for Completing the Serious Adverse Report Form. Once the EDC system is functional, the SAE report should be retrospectively added to the EDC system and follow-up should be completed through the EDC. The original copy of the Serious Adverse Event Report Form and the email or facsimile confirmation sheet must be kept at the study site (refer to the Incyte Reference Guide for Completing the Serious Adverse Report Form or Study Reference Manual for details and for the email address or fax number).
- Follow-up information is also recorded in the eCRF and transmitted to Incyte Pharmacovigilance via the EDC system. The follow-up report should include information that was not provided previously, such as the outcome of the event, treatment provided, action taken with study cream because of the SAE (eg, dose reduced, interrupted, or discontinued), or participant disposition (eg, continued or withdrew from study participation). Each recurrence, complication, or progression of the original event should be reported as follow-up to that event, regardless of when it occurs.
- Contacts for SAE reporting can be found in the Study Reference Manual.

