Pregnancy testing	X	X*			X	Section 8.4.4.2; at the indicated visits, only female participants who have reached menarche will undergo a urine pregnancy test. A positive urine test must be confirmed by a serum test. *Day 1 testing will be performed only if the interval between this visit and screening is > 2 weeks.	

Table 3: Schedule of Activities: Vehicle-Controlled Period (Continued)

Visit Day (Range)	Screening	VC Period				Notes and Protocol Section
	Days -28 (+ 7 ^a) to -1	Day 1/ Baseline	Wk 2 (± 3 d)	Wk 4 (± 3 d)	Wk 8 ^b /ET (± 3 d)	

Note: Unscheduled visits may occur at any time at the investigator's discretion, and appropriate clinical and laboratory tests may be performed as clinically indicated.

^a For prior medications that require a 4-week washout period (see Section 5.2, Exclusion Criterion 6b), a 35-day screening period is allowed.

^b Week 8 is the baseline for participants eligible to continue in the LTS period (IGA score = 0-4 and BSA = 0%-20%).

Table 4: Schedule of Activities: Long-Term Safety Period

Visit Day (Range)	LTS Period					Unscheduled Visit	Safety Follow-Up 30 (+ 7) Days After Last Study Cream Application ^a	Notes and Protocol Section
	Wk 12 (± 7 d)	Wk 16, 20, and 24 (± 7 d)	Wk 28, 32, and 36 (± 7 d)	Wk 40, 44, and 48 (± 7 d)	Wk 52/ EOT/ET (± 7 d)			
Administrative procedures								
Contact IRT	X	X	X	X	X	X	X	Section 8.1.3.
Prior/concomitant medications and procedures	X	X	X	X	X	X	X	Section 6.6.
Apply study cream at site	X	X	X	X				Section 6.1; only for participants with active AD lesions at time of visit; apply the first (morning) application under direct site staff supervision.
Weigh and dispense study cream; dispense diary cards	X	X	X	X				Section 6.1 and Section 8.1.4.
Collect and weigh study cream; collect diary cards	X	X	X	X	X			Section 6.1.
Record start and end dates of treatment cycle(s)	X	X	X	X	X			Section 6.1; the start/end date will have been recorded by the participant. The end date should be 3 days after lesions clear; however, if this 3-day window is during a study visit and IGA score = 0, stop treatment and record the date of the study visit as the treatment cycle end date.
Assess compliance	X	X	X	X	X			Section 6.4.
Safety assessments								
AE assessments	X	X	X	X	X	X	X	Section 8.4.1.
Comprehensive physical examination					X			Section 8.4.2.1.

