4. STUDY DESIGN

4.1. Overall Design

This is a randomized, double-blind, VC study with an LTS period in pediatric participants with AD eligible for topical therapy, to be conducted at approximately 60 sites in the United States and Canada. For participants who meet all study inclusion criteria and none of the exclusion criteria, study cream will be assigned at the Day 1/baseline visit. Participants will be randomized 2:2:1 to blinded treatment with ruxolitinib cream 0.75% BID, ruxolitinib cream 1.5% BID, or vehicle cream BID, with stratification by baseline IGA score and age. Enrollment will be capped such that no more than approximately 25% of randomized participants have a baseline IGA score of 2. At least 40% of the overall study population will consist of children aged \geq 2 years to 6 years.

During the 8-week VC period, participants will apply study treatment BID to all areas identified for treatment at the Day 1/baseline visit even if the AD begins to improve and lesions decrease in size. Note: Throughout this protocol, the term "participant" refers either to the participants themselves or, in the case of younger children, their parent or legal guardian.

At Week 8, efficacy (the primary endpoint of the study) will be evaluated as the proportion of participants achieving treatment success (IGA score of 0 or 1 with \geq 2-grade improvement from baseline).

Participants who complete Week 8 assessments with no additional safety concerns will continue into the 44-week LTS period with the same treatment regimen, except those initially randomized to vehicle cream will be rerandomized (1:1) in a blinded manner to 1 of the 2 active treatment groups (ruxolitinib cream 0.75% or 1.5% BID). The IGA score required for participants to enter the LTS period is 0 to 4, and participants must have a %BSA in the range of 0% to 20% (excluding the scalp).

During the LTS period, participants will have study visits every 4 weeks until the end of the study (52 weeks total). At each of these visits, including Week 8 (baseline visit for the LTS period), the participant's AD lesions will be evaluated by the investigator to determine whether the participant requires continuation of treatment or should (re)enter an observation/no treatment cycle. If the IGA score is \geq 1, the participant will start or continue active treatment with ruxolitinib cream (0.75% or 1.5%) BID. If the IGA score is 0 (clear), the participant will (re)enter an observation/no treatment cycle.

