8.4.1. Adverse Events

Adverse events will be monitored from the time the participant signs the ICF (or assent) until at least 30 days after the last application of study cream. Adverse events that begin or worsen after informed consent should be recorded on the Adverse Events Form in the eCRF regardless of the assumption of a causal relationship with the study cream. Conditions that were already present at the time of informed consent should be recorded on the Medical History Form in the eCRF. Adverse events (including laboratory abnormalities that constitute AEs) should be described using a diagnosis whenever possible rather than by individual underlying signs and symptoms.

Adverse events will be reported by the participant (or, when appropriate, by a caregiver, surrogate, or the participant's legally authorized representative). The investigator and any qualified designees are responsible for detecting, documenting, and recording events that meet the definition of an AE or SAE and remain responsible for following up on AEs that are serious, considered related to the study cream/procedures, or that caused the participant to discontinue the study cream. Care will be taken not to introduce bias when detecting AEs and/or SAEs.

Open-ended and nonleading verbal questioning of the participant, such as "How are you feeling?", is the preferred method to inquire about AE occurrences. Adverse events may also be detected when they are volunteered by the participant during the screening process or between visits or through physical examinations, laboratory tests, or other assessments. The definition, reporting, and recording requirements for AEs are described in Section 9.

All SAEs will be reported to the sponsor or designee within 24 hours. The investigator will submit any updated SAE data to the sponsor within 24 hours of it being available.

After the initial AE/SAE report, the investigator is required to proactively follow each participant at subsequent visits/contacts. All SAEs will be followed until resolution, stabilization, the event is otherwise explained, or the participant is lost to follow-up (as defined in Section 7.3).

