8.9. Follow-Up

8.9.1. Safety Follow-Up

The safety follow-up period is the interval between the Week 52/EOT or ET visit and the scheduled follow-up visit, which should occur 30 days after the Week 52/EOT or ET visit, with the following 2 exceptions:

- Follow-up visit should occur at the Week 52/EOT visit for participants who have been in an observation/no treatment cycle with an IGA score of 0 (clear) from Week 48 or earlier until Week 52
- Follow-up visit should occur 30 days after the last application of study cream if the Week 52/EOT or ET visit was not performed.

Adverse events and SAEs must be reported up until 30 days after the last application of study cream; ongoing AEs and SAEs must be followed up until toxicities resolve, return to baseline, or are deemed irreversible, whichever is longer. Reasonable efforts should be made to have the participant return for the follow-up visit and report any AEs that may occur during this period.

9. ADVERSE EVENTS: DEFINITIONS AND PROCEDURES FOR RECORDING, EVALUATING, FOLLOW-UP, AND REPORTING

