10.4.3. Safety Analyses

A TEAE is any AE either reported for the first time or worsening of a pre-existing event after the first application of study cream. Analysis of AEs will be limited to TEAEs, but data listings will include all AEs regardless of their timing to study cream administration. AEs will be tabulated by the MedDRA preferred term and system organ class. Severity of AEs will be based on the National Cancer Institute CTCAE v5.0 using Grades 1 through 5.

The subset of AEs considered by the investigator to have a relationship to study cream will be considered to be treatment-related AEs. If the investigator does not specify the relationship of the AE to study cream, then the AE will be considered treatment-related. The incidence of AEs and treatment-related AEs will be tabulated.

The clinical laboratory data will be analyzed using summary statistics; no formal treatment group comparisons are planned. Laboratory test values outside the normal range will be assessed for severity based on the normal ranges for the clinical reference laboratory. The incidence of abnormal laboratory values and shift tables relative to baseline will be tabulated.

Descriptive statistics and mean change from baseline will be determined for vital signs (blood pressure, pulse, respiratory rate, and body temperature), height, and weight at each assessment time.

[REDACTED]

[REDACTED]

[REDACTED]

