9.2. Adverse Events

9.2.1. Adverse Event Definitions

A TEAE is any AE either reported for the first time or worsening of a pre-existing event after first application of study drug and within 30 days after the last dose of study drug. For participants who cross over treatments, the first application date is period specific, and the end date is 30 days after the last application date in this period or the first application date in the next period, whichever comes first. Analysis of AEs (as discussed below) will be limited to TEAEs, but data listings will include all AEs regardless of their timing in relation to study drug administration.

Adverse events will be tabulated by MedDRA PT and SOC. Severity of AEs will be graded using the NCI CTCAE v5. The CTCAE (Grade 1 to 5) is used for this study. The CTCAE reporting guidelines and grading details are available on the Cancer Therapy Evaluation Program website.

The subset of AEs considered by the investigator to be related to study drug will be considered treatment-related AEs. If the investigator does not specify the relationship of the AE to study drug, the AE will be considered treatment-related. The incidence of AEs and treatment-related AEs will be tabulated. In addition, serious AEs will also be tabulated.

Any missing onset date, causality, or severity must be queried for resolution. Unresolved missing causality and severity will be handled according to the following rules:

- An unresolved missing causality will be considered treatment-related.
- An unresolved missing severity will be identified as an unknown severity.

For purposes of analysis, all AEs will be considered TEAEs unless the AE can unequivocally be defined as not treatment-emergent.

Application site reactions are AEs that occur at the site of drug application. A summary of ASRs will be provided. Exposure-adjusted summaries will also be provided for the safety population, including cumulative TEAEs and cumulative ASRs.

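### SAP 9.2.1 adds a 30-day TEAE cut-off that the protocol definition lacks, so late events in untreated LTS children drop out of the safety summaries; the protocol's AE/SAE reporting windows also contradict each other

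*Protocol*

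**What the plan says.** **Design.** Under Protocol 4.1, participants who complete Week 8 without additional safety concerns "will continue into the 44-week LTS period with the same treatment regimen", except that vehicle children are rerandomized to one of the two strengths. "If the IGA score is 0 (clear), the participant will (re)enter an observation/no treatment cycle". This can happen from the Week 8 visit onward, and cream is restarted at recurrence. Visits continue every 4 weeks to Week 52. In Table 4 the row "AE assessments" is marked at every LTS visit, at unscheduled visits and at safety follow-up, whether or not the child is using cream.

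**Analysis window.** Protocol 10.4.3: "A TEAE is any AE either reported for the first time or worsening of a pre-existing event after the first application of study cream". It gives no end date. SAP 9.2.1 requires the event to fall "after first application of study drug and within 30 days after the last dose of study drug". For children who cross over, the SAP makes the window period-specific: it closes 30 days after the last application in the period, or at the first application in the next period if that is sooner. AE analysis is restricted to TEAEs, while listings keep all AEs. SAP 11.1 records no change to protocol-defined analyses.

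**Reporting window.** The first paragraph of Protocol 9.4 says that SAEs after consent "through 30 days after the last application of study cream, must be reported to the sponsor (or designee) within 24 hours". Section 8.9.1 says: "Adverse events and SAEs must be reported up until 30 days after the last application of study cream". Section 8.4.1, however, monitors AEs "until at least 30 days after the last application of study cream" and sends all SAEs to the sponsor within 24 hours. Section 9.3 records any AE or SAE beginning after consent, with no end date. The reporting box in 9.4 covers any SAE, again with no end date.

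**The concern.** A 30-day tail suits a design in which treatment stops once and follow-up then ends. Here treatment stops and starts, and a child can remain on study without cream for months. The date of the last dose is known only in retrospect, so the TEAE status of an off-treatment event is settled by whether the child relapses later. Among active-arm children, events that occur long after the last application are lost from the summaries only in those who stay clear.

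At stake is the purpose of the LTS period, which Protocol 2.3.1 describes as safety information under longer, intermittent use. SAP 9.2.2 names malignancies, major cardiovascular events and thromboembolic events as events of interest. These are rare, so one case missing from a summary table matters. Omission follows sustained clearance, so it could also differ between strengths, although the documents give no evidence that it would.

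On the reporting side, sites have two sets of instructions for SAEs in untreated children who are still on study.

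**Working it through.** **Check on the time frame.** Protocol 4.2 gives total participation of about 61 weeks. Screening 28 + 7 = 35 days, VC period 8 × 7 = 56, LTS period 44 × 7 = 308, follow-up 30. Sum: 35 + 56 + 308 + 30 = 429 days, and 429 / 7 = 61.3 weeks. The stated figure is reproduced.

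**Time outside the TEAE window.** Week w is nominally Day 7w + 1 (SAP 6.3 puts Week 8 at Day 57), so Week 52 is Day 365. If the last application is at week w and the child stays clear, the window closes on Day 7w + 31. On-study days outside it = 365 − (7w + 31), floored at 0.

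| Last application | Day | Window closes | Days outside, to Week 52 | Share of 308 LTS days |
|---|---|---|---|---|
| Week 12 | 85 | 115 | 250 | 81% |
| Week 24 | 169 | 199 | 166 | 54% |
| Week 36 | 253 | 283 | 82 | 27% |
| Week 44 | 309 | 339 | 26 | 8% |
| Week 48 | 337 | 367 | 0 | 0% |

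In the Week 12 case, the Week 16 visit (Day 113) is still inside the window. The nine visits from Week 20 to Week 52 are outside it, and Table 4 requires an AE assessment at each.

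**Dependence on later treatment.** Take two children on the same active cream, both treated up to Day 85 and both with an event on Day 145, 60 days off cream.

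- Child A re-treats on Day 200 (illustrative). The window now closes no earlier than 200 + 30 = Day 230. Day 145 is inside, so the event is a TEAE.
- Child B stays clear. The window closed on Day 115. Day 145 is outside, so the event is not a TEAE.

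The events and the treatment history up to Day 145 are identical; only what happened afterwards differs.

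**Vehicle children.** Take a vehicle child with IGA 0 at Week 8. Table 3 gives no application at that visit, so the last vehicle application is on Day 56 and the vehicle window closes on Day 56 + 30 = Day 86. Suppose the first ruxolitinib application is at Week 20, Day 141 (illustrative). Days 87 to 140, that is 140 − 86 = 54 days, belong to neither period's window, even though treatment starts later.

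**Where a late event can appear.** The AE summaries in SAP 9.2.2 and Appendix A, including those for SAEs, events of interest and the Baseline to Week 52 set, are built on TEAEs. A dated event beyond 30 days therefore reaches only listings such as 2.7.1, 2.7.3 and 2.7.9. The SAP default that an AE is treatment-emergent unless clearly not so does not help when the date is known. A child who applies no cream in the LTS period is also outside the LTS evaluable population (SAP 5.3.5). That child's events could be summarized only in the Baseline to Week 52 tables, and those tables are titled for children who used ruxolitinib throughout.

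**Reporting sections side by side.** Stop at 30 days after the last application: first paragraph of 9.4, and 8.9.1. Do not stop there: 8.4.1 (30 days is a minimum), 9.3, the 9.4 box, and Table 4, which the protocol summary makes mandatory.

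**The case against.** A reader might infer from 9.4 that an SAE in a child more than 30 days off cream need not be reported within 24 hours unless judged related. The documents do not support this. The related-only sentence concerns the time after study participation has concluded and the child has been discharged. A clear child attending visits every 4 weeks is neither. Section 4.2 counts a participant as having completed only after all visits, including safety follow-up. The parenthesis in 9.4 that equates the end of participation with 30 days after the last application invites the misreading, but the discharge condition remains. The 8.9.1 sentence also sits in a section about the period after Week 52 or early termination. Section 6.5 treats clearance in the LTS period as a temporary interruption, and a site cannot know at the time that an application was the last. A careful site would probably go on reporting. All of this stands, and it reduces the reporting half to a contradiction in wording.

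The amendment summary shows that Amendment 5 removed the last study visit as an end point for SAE reporting, for alignment with other sections. That explains the wording, but the sections listed above are still not aligned.

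On the SAP half, a 30-day window is a common convention, late events remain in the listings, and some would hesitate to call an event months after a topical cream treatment-emergent. These points are fair. They do not answer the undeclared departure from Protocol 10.4.3, nor the fact that the same off-treatment event is counted or not according to later relapse. If events long after the last application are to be excluded, the exclusion should apply equally to children who restart.

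**Conclusion.** The SAP point holds. SAP 9.2.1 narrows the protocol's TEAE definition without declaring it. With observation cycles built in, this makes an active-arm child's inclusion in the safety summaries depend on later re-treatment, and it leaves an uncovered interval for some vehicle children. For a child last treated at Week 12, 250 on-study days are outside the window; the figure falls to 0 for a last application at Week 48. These figures assume nominal visit days and no re-treatment. AD recurs, so long untreated spans may be uncommon. The documents do not give the number of children concerned, and no estimate is offered here.

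The reporting point holds only as an inconsistency: 9.4 paragraph 1 and 8.9.1 conflict with 8.4.1, 9.3, the 9.4 box and Table 4. Two further inferences go too far. Late events do not vanish, because recorded ones are listed. Nor is a restarting child's event always counted, as the vehicle case shows.

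**What to change.** 1. In SAP 9.2.1, count on-study LTS events up to the later of the last study visit and 30 days after the last application, in line with Protocol 10.4.3. If the 30-day end is kept, declare it in SAP 11.1.
2. Flag every event that starts more than 30 days after the most recent application, whether or not treatment restarts. Show SAEs and events of interest with and without flagged events.
3. Show separately the interval between the end of the vehicle window and the first ruxolitinib application, and state where events are summarized for children who apply no cream in the LTS period.
4. Align 9.4 paragraph 1 and 8.9.1 with 8.4.1, 9.3, the 9.4 box and Table 4, so that AE and SAE reporting runs to the later of the last study visit and 30 days after the last application.

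The cost is wording in both documents and one derived flag from treatment-cycle dates that Protocol 4.1 already collects. No visits are added. LTS event counts would rise slightly and would include some off-treatment events, which the flag separates. The exposure-adjusted summaries would need a time base with the same end, because SAP 6.4 ends treatment duration at the last recorded application.
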